
Neuroinflammation and accompanying neurocognitive dysfunction is also a major clinical issue in HIV infection, and is exacerbated by concomitant MA abuse. HIV-associated neurocognitive disorders (HAND) are common even with antiretroviral therapy, with 52% of patients in a recent HIV clinical cohort exhibiting at least some level of neuropsychological impairment (Heaton, Clifford et al. 2010). HIV does not directly infect CNS neurons and HAND is thought to result primarily from the infection and subsequent activation of CNS macrophages and microglia, which then secrete many of the same pro-inflammatory cytokines that are also secreted in response to MA including TNF- α , IL-1 β , IL-6, and MCP-1 (Yadav and Collman 2009). HIV proteins gp120 and Tat are also neurotoxic and combined with MA exhibit synergistic toxicity on striatal dopaminergic neurons and the blood-brain barrier leading to enhanced CNS penetration by HIV (Silverstein, Shah et al. 2011). Not surprisingly, MA abuse increases the risk for neurocognitive impairment among HIV infected persons (Rippeth, Heaton et al. 2004, Carey, Woods et al. 2006), especially with HIV/HCV co-infection (Cherner, Letendre et al. 2005, Letendre, Paulino et al. 2007). Greater cognitive dysfunction is associated with poor HIV clinical outcomes including medication non-adherence (Becker, Thames et al. 2011) and worse quality of life (Parsons, Braaten et al. 2006). Therefore, medications that reduce neuroinflammation in HIV infected MA users may improve HIV and MA-related clinical outcomes via improvements in neurocognitive functioning.

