"Drop-out" Subject Tracking: Subjects who have not rescinded consent, but are no longer available/interested in attending twice-weekly visits ("drop-outs") will be followed using alternative methods. Every effort will be made for all subjects in the trial to attend a minimum of one clinic visit a week. However, attrition in Phase 2 trials tends to be high. In order to comprehend the reasons for dropping out of the clinical trial, we will arrange to meet the research subject weekly during the course of the medication phase of the trial at a mutually-agreeable location and/or taxi the participant to the clinic to collect a urine drug sample and complete data typically collected on a weekly basis.

Termination and Follow-Up Procedures: Once participants complete the 12-week medication period, they will be asked to return during week 13 for a repeat EKG, labs, and physical exam, and for follow-up assessment. On the final visit (approximately 30 days after completing study medications), participants will complete a brief health check with a study clinician. Every effort will be made to retain all participants through the entire trial. Our group has developed effective procedures for retaining individuals in controlled experimental drug trials (e.g., building strong relationships with study participants, telephone, texting, and letter procedures). Similar strategies will be implemented for this proposed study. However, we recognize that not all participants will complete the trial. Early termination criteria by the principal investigator are defined as two consecutive weeks (or four consecutive visits) of missed study activity or data collection visits. Participants who end the trial early, for whatever reason, will be asked to attend the 4-week follow-up visits.

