Plasma and serum will be collected during the lead-in period and during weeks 3, 8 and 13 to measure inflammatory and neurotrophic markers. Plasma levels of the following inflammatory cytokines and chemokines will be determined via multiplex assay: IFN- α , IL-1 β , IL-2, IL-6, TNF- α , MCP-1, MIP-1 α , MIP-1 β , and MIF. Serum levels of neurotrophic factors, GDNF and BDNF, will be determined via singleplex assays. In addition to the above markers, CRP and uric acid will also be measured from serum at baseline and weeks 3, 8 and 13 via ELISA and Uricase assays, respectively. Potential changes in inflammatory markers with treatment for MA dependence will be assessed.

Neuropsychological Assessment: A battery of neuropsychological (NP) tests will be administered to approximately half of the sample (N = 70) at baseline, week 4, and immediately following discontinuation of study medication (week 13). As acute stimulant use masks neurocognitive deficits in stimulant abusers (Woicik, Moeller et al. 2009), participants will receive gift cards for providing methamphetamine-free urine samples during the second week of the lead-in period when baseline cognitive testing will be done. Any potential confounding effect of MA use on cognitive battery results will be explored in the data analysis.

In addition to the comprehensive pre- and post-medication NP battery, brief serial assessments will be administered during the medication treatment period (weeks 1-12) to examine potential changes in both top-down (Iowa Gambling Task) and bottom up (Stop Signal test) cognitive processing approaches during treatment. The Connors' CPT will be administered on weeks 2, 6 and 10.

Note: Collection of data for the neurocognitive battery was concluded after randomization of 85 participants due to staff and budgetary constraints.

Subject Reimbursement: Subjects will be reimbursed for time spent completing study measures and costs related to transportation to and from the clinic in the form of gift cards only; no cash is provided to subjects (Table 4).

Table 4: Potential Participant Reimbursement with neurocognitive testing (pre- July 2016)

Activity	Amount
CM intervention during lead-in (\$15 for the first MA-free urine, \$25 for second, and \$40 for third)	\$80
Completion of screening measures	\$25
Completion of Medication adherence check (\$5/week x 12 weeks)	\$60
Twice-weekly clinic attendance during weeks 1-10 (\$10/visit x 20 visits)	\$200

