Neurocognitive testing will be performed on the initial 85 participants enrolled. Beginning in July 2016 (N = 85) only the MOCA will be administered at baseline and again at weeks 4 and 13. While we will include selected clinical NP tests to allow characterization of traditionally studied NP domains and to facilitate cross-study comparisons, our assessment strategy is focused on elucidation of underlying neurocognitive endophenotypes that are associated with chronic MA use and/or may serve as barriers to optimal engagement in treatment. We will employ tasks that are sensitive to disordered inhibitory control, risky decision making, attentional control, and procedural learning and probabilistic categorization. When feasible, clinical NP tests that are part of the MATRICS battery will be employed. The MATRICS battery (an acronym for Measurement and Treatment Research to Improve Cognition in Schizophrenia) is the product of an NIMH initiative to stimulate the development of pharmacological agents to treat NP deficits in schizophrenia. It is specifically designed to be used in clinical trials in which

it is crucial to measure cognitive change in a short period of time with good test-retest reliability, relationship to functional outcome, and tolerability (MATRICS Manual, 2006). While there are of course significant differences between the cognitive deficits seen in schizophrenia vs. MA dependence, there is also considerable overlap, making this test battery particularly well-suited for this study. We will also include NP tests that measure cognitive functions thought to be relatively unaffected by MA use (i.e., language, visuospatial processing) to evaluate the specificity of our measures.

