During weeks 4 and 13, participants will repeat the following tasks: Montreal Cognitive Assessment; MATRICS CPT-II; HVLIT-R; BVMT-R; SST; TMT; DDT; WAIS-IV Letter Number Sequencing ; WAIS-IV Symbol Search, WAIS-IV Digit Symbol Coding; N-Back Task; DKEFS Color Word Interference and the Iowa Gambling Task.

Data Analysis: The primary objective of this study is to determine the efficacy of IBUD as a treatment for MA dependence and to provide FDA with sufficient data to advise whether IBUD should move forward for marketing as a MA dependence treatment. The primary outcome variable is the FDA-specified criterion of significant MA abstinence at the end of treatment defined as no self-reported MA use during the final two weeks of treatment (weeks 11/12) confirmed via urine drug screens (at least one of the two possible urine specimens each week is available during weeks 11 and 12 and all available urine specimens are MA-negative). The study is powered to detect a significant difference in the proportion of participants achieving this outcome in the IBUD versus placebo groups. Additional measures of clinically meaningful reductions in MA use during treatment will also be assessed in the event that IBUD produces effects on MA use that do not meet the abstinent at end of treatment threshold. In addition to MA use outcomes, treatment retention, an important clinical variable that is associated with long-term treatment outcomes in substance abuse treatment (Hser, Evans et al. 2004), with IBUD versus placebo will be compared. Effects of potential confounders on each of these outcomes will also be examined including: (1) medication non-adherence, (2) medication safety and tolerability (adverse event rates), and (3) ability to achieve initial MA abstinence with the CM intervention during the two week lead-in period.

A general univariate strategy will be used to test for differences between conditions at baseline and along all outcome variables using bivariate analyses (i.e., t-tests/ANOVA for continuous variables; χ^2 for dichotomous variables). A multivariate analysis will also be used when appropriate to control for co-variables known to influence MA dependence treatment outcomes including age, gender, baseline severity of MA dependence, HIV status, and ability to achieve initial abstinence during the CM lead-in.

Aim 1: To determine whether IBUD reduces MA use more than placebo among MA dependent participants.

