Hypothesis 3: IBUD will result in greater improvements in CD4 count, HIV viral load, and neurocognitive functioning than placebo among HIV positive participants.

Analysis: Change scores for CD4 count, HIV viral load, and scores on neurocognitive assessments will be calculated between baseline and end of medication treatment. The mean change score for each measure will be calculated for IBUD versus placebo. A linear regression model will be used to assess the mean change in measures for IBUD versus placebo after controlling for possible confounders such as gender, MA abstinence during the two-week lead-in period, and medication adherence.

Aim 4: To determine whether IBUD improves behavioral outcomes (sexual transmission behaviors; uptake and/or adherence to HIV medications) relative to placebo among HIV-positive MA dependent participants.

Hypothesis 4: IBUD will result in greater reductions in HIV risk behaviors and increased HIV medication uptake/adherence than placebo among HIV positive participants.

Analysis: The proportion of participants reporting HIV sexual risk behaviors in the IBUD and placebo groups will be calculated. The proportion of participants reporting receipt of HIV medications as well as the proportion of medication they report taking will be calculated. The mean number of self-reported HIV

[figure not shown]
sexual risk behaviors for IBUD versus placebo will be compared via t tests and then in a linear regression model controlling for potential confounders. The mean HIV medication adherence rate (proportion of medication taken) for IBUD and placebo will also be compared via t test and then linear regression model.

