Exploratory analyses Baseline neurocognitive functioning of participants will be described using results of the neuropsychiatric (NP) battery performed at baseline. Baseline to post-treatment changes in scores on tests in the NP battery will be calculated for IBUD and placebo groups. Effect sizes for IBUD on NP battery change scores will be calculated and used to determine whether future fully powered studies examining NP changes with IBUD are warranted. In addition, GEE models will be used to compare change in the brief serial weekly cognitive assessments (Balloon Analog Reaction Time task and Stop Signal test) during treatment with IBUD versus placebo. To explore whether severity/type of neurocognitive dysfunction at treatment entry mediates response to IBUD, baseline scores on NP assessments will be included as co-variables in the models assessing IBUD effects on MA use outcomes and treatment retention. Finally, potential effects of polymorphisms in dopaminergic genes and GDNF (Yoshimura, Usui et al. 2011), as well levels of inflammatory biomarkers and neurotrophic factors on treatment outcomes will be explored. The sample will be stratified by genotype for each SNP and changes in MA use and retention for IBUD versus placebo will be compared in these sub-groups. In addition, baseline versus post-treatment serum and plasma levels of inflammatory markers neurotrophic factors will be compared for IBUD versus placebo groups and by HIV serostatus. Correlation between early life stress measures and baseline severity of MA abuse as well as treatment outcomes, including potential early life stress-ibudilast interactions, will also be explored.

We recognize that the study is not powered to detect statistical significance in these analyses, especially if corrections for multiple testing are employed (Benjamini and Hochberg 1995) and as a result these analyses are by design for exploratory purposes only. Still we feel that including these probes of potential IBUD mechanisms of action within the context of this early clinical trial is important in that the results may bolster any observed effects of IBUD on MA use outcomes and direct the design of subsequent adequately powered confirmatory phase III trials.

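### The neuropsychological battery is analysed as a two-point change score: week-4 data go largely unused, and participants without a final battery drop out with no missing-data plan

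*Combined protocol and SAP*

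**What the plan says.** **Schedule.** The Neuropsychological Assessment section places the battery "at baseline, week 4, and immediately following discontinuation of study medication (week 13". The section on neurocognitive endophenotypes says "During weeks 4 and 13, participants will repeat the following tasks" and lists 13 tasks; Appendix II shows the same visits. On numbers: "Neurocognitive testing will be performed on the initial 85 participants enrolled". After July 2016 only the MoCA continues.

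**Analysis.** Two places in Data Analysis deal with the battery by arm.
- Exploratory analyses: "Baseline to post-treatment changes in scores on tests in the NP battery will be calculated for IBUD and placebo groups". The resulting effect sizes are to decide whether fully powered cognition studies are warranted.
- Aim 3, HIV-positive participants: "Change scores for CD4 count, HIV viral load, and scores on neurocognitive assessments will be calculated between baseline and end of medication treatment". A linear regression follows. The covariates it names as examples do not include the baseline score.

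The exploratory paragraph also plans a longitudinal analysis: "GEE models will be used to compare change in the brief serial weekly cognitive assessments (Balloon Analog Reaction Time task and Stop Signal test".

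**Loss to follow-up.** *Drop-out Subject Tracking* says: "However, attrition in Phase 2 trials tends to be high". It gives no rate. Weekly tracking of drop-outs collects urine and the weekly measures, and the battery is not one of these. *Termination and Follow-Up Procedures* asks people who end early to attend the follow-up visits. The only missing-data rule, in Power calculations, treats missing as non-abstinent for the primary outcome. None is given for cognitive scores.

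**The concern.** A change from baseline to the final battery exists only for people who have a final battery. Those tested at baseline and week 4 but not at the end contribute nothing to it, although their week-4 scores have been collected.

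The plan gives reason to think this loss may be neither random nor equal between arms. Hypothesis 2 predicts longer retention on IBUD. The Background lists neurocognitive dysfunction and poor response to behavioural therapy together as consequences of methamphetamine neurotoxicity. For HIV it says: "Greater cognitive dysfunction is associated with poor HIV clinical outcomes including medication non-adherence". If staying is related both to cognition and to arm, the change score compares two differently selected groups.

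At stake is the effect size that feeds the decision on further cognition studies. The primary abstinence outcome, the sample size and safety are not affected.

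**Working it through.** **1. Coverage of week 4.** Thirteen tasks are listed as repeated at weeks 4 and 13. The GEE names two tasks: the Stop Signal test, which is in the battery, and a Balloon Analog task, which is in neither the measures list nor Appendix II. That leaves 13 − 1 = 12 repeated tasks with no stated between-arm use of week 4. The Neuropsychological Assessment section names the Iowa Gambling Task as the other serial task. If that is what was meant, 11 remain. Appendix II does not schedule either task weekly.

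**2. How many people this touches (assumed rates).** Suppose 85% are tested at week 4 and 51–65% at week 13, with everyone tested at week 13 also tested at week 4. Then 85 − 65 = 20% to 85 − 51 = 34% have a week-4 but no final battery. Of 85 people that is 0.20 × 85 = 17 to 0.34 × 85 ≈ 29.

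**3. Precision with completers only.** Half-width of the 95% interval for a standardised difference ≈ 1.96 × √(2/n per arm):
- no loss, 42.5 per arm: 0.43
- 20% without a final battery, 34 per arm: 0.48
- 50% without a final battery, about 21 per arm: 0.60

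**4. Bias.** Simulated trials of n = 84 with a true effect of 0.40 SD at weeks 4 and 13, between-visit correlation 0.6–0.7 and the testing rates in step 2. The odds of being retained are multiplied by 2.7 per SD of the variable in the first column, and by 1.0 or 1.8 for IBUD. With Y0, Y4 and Y13 the scores at baseline, week 4 and week 13, the estimators are:
- change score: difference between arms in mean (Y13 − Y0) among those with Y13;
- likelihood estimate using week 4: arm coefficient for Y13 given arm, Y0 and Y4, plus (Y4 coefficient × arm coefficient for Y4 given arm and Y0).

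| Retention depends on | Direct arm effect on retention | Change score | Using baseline and week 4 |
|---|---|---|---|
| week-4 improvement | none | 0.37–0.38 | about 0.40 |
| week-4 improvement | odds × 1.8 | 0.33–0.36 | about 0.40 |
| baseline score | none | 0.40 | about 0.40 |
| baseline score | odds × 1.8 | 0.42–0.44 | about 0.40 |

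The last column stays within 0.39–0.41 throughout. A baseline-adjusted regression in completers gives 0.36–0.37 in the second row and 0.40 in the last two. A rerun of all these scenarios for this note agreed.

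A second set of assumptions (true effect 0.30, correlation 0.6) fixes the dropout fraction in each arm. Equal dropout leaves the change score at 0.30. So does unequal dropout unrelated to the score. With 50% dropout on placebo against 30% or 20% on IBUD, related to week-4 change, it falls to between 0.25 and 0.16; using week 4 returns 0.30.

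**5. Size against noise.** Worst downward case in step 4 (correlation 0.6, 51% tested at week 13, odds × 1.8): the means are 0.333 for the change score, 0.359 for baseline-adjusted completers and 0.402 using week 4. The standard errors are 0.278, 0.254 and 0.250.
- Bias of the change score: 0.400 − 0.333 = 0.067, and 0.067/0.278 = 0.24 of one standard error.
- Reduction in standard error, change score to week-4 model: 1 − 0.250/0.278 = 10%. Across scenarios it is about 6–11%.
- Root-mean-square error, √(bias² + SE²): √(0.067² + 0.278²) = 0.286; √(0.041² + 0.254²) = 0.257; √(0.002² + 0.250²) = 0.250.

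**The case against.** Four stronger readings are tempting, and the documents do not support them.
- *Cognition is analysed only by change score, and week 4 is unused.* The GEE on serial tasks is a longitudinal analysis, and it names the Stop Signal test, which is in the week-4 battery.
- *Everyone who leaves before week 13 is excluded.* Early leavers are asked back, so only those without a final battery are lost. That loss follows from how a change score is defined; no exclusion rule is stated.
- *The bias shrinks a real IBUD benefit.* This holds if retention follows week-4 improvement. The Background statements concern the level of dysfunction, and one of them concerns adherence in HIV. Retention driven by baseline cognition gives no bias or an upward one.
- *The decision on future studies would change.* The plan sets no threshold, so this cannot be shown.

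It is also fair to say that the analyses are declared exploratory and unpowered, that most of the gain comes from baseline adjustment (root-mean-square error 0.286 to 0.257, then 0.250 with week 4, a further 3% or so), and that full recovery in the simulations is by construction, because loss was generated as missing at random.

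What stands: 11 or 12 repeated tasks have no stated between-arm use of week 4, the change score loses people without a final battery, and no missing-data method is given for these scores.

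**Conclusion.** The point holds as a low-severity improvement. The two-point change score leaves most of the week-4 battery out of the between-arm analysis and depends on who returns for a final battery, in a trial that expects high attrition and hypothesises an arm difference in retention.

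Under the assumed dropout models it averages about 0.33 to 0.44 against a true 0.40, that is, from 17% low to 10% high. Bias of this size is about a quarter of a standard error at most, and its direction is not established. The second set of assumptions, with dropout rates fixed and very unequal between arms, gives larger downward shifts. The gain in precision, a standard error about 6–11% smaller, appears whichever way the bias runs. All these sizes rest on assumed rates, correlations and retention odds, because the documents supply none.

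**What to change.** In Data Analysis, under Aim 3 and Exploratory analyses, replace the change score for the neuropsychological tests with a mixed model for repeated measures:
- outcome: week-4 and week-13 scores;
- terms: arm, visit, arm-by-visit and baseline score;
- population: every participant with a baseline and at least one later battery.

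Report the arm difference at each visit, and take the effect size used to decide on future studies from the week-13 contrast. CD4 count and viral load have no week-4 measurement and are outside this change. Separately, reconcile the serial tasks named for the GEE with the measures list and Appendix II.

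The cost is a revision of the analysis text; all the visits are already scheduled. The downside is an assumption that scores are missing at random given baseline and week-4 scores. That is weaker than what the completer change score needs, but it gives no protection if loss depends on decline after week 4, and people lost before week 4 still contribute nothing.

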Our brief serial assessments will include tests that target bottom-up and top-down cognitive processing approaches. Prior work has demonstrated that successful abstainers may attempt to control their intrusive drug-related cognitions either by diverting their attention away from drug-related stimuli (Baker, Lee et al. 2005, Kavanagh, Andrade et al. 2005, Schoenmakers, de Bruin et al. 2010) or suppressing their subjective craving (Brody, Mandelkern et al. 2007), an effect which may be facilitated by increased top-down cognitive processing. Similarly, drug-dependent individuals may demonstrate deficits in top-down cognitive processing, concomitant with increased bottom-up activity in such regions as the nucleus accumbens and amygdale (Due, Huettel et al. 2002, David, Munafò et al. 2005, McClernon, Hiott et al. 2007) which trigger the affective and appetitive signals of immediate drug outcomes (Bechara 2005). This may suggest that in successful abstainers, there will be increased top-down processing in areas responsible for cognitive control, error/ risk detection (Whalen, Bush et al. 1998, Bush, Luu et al. 2000, Bechara 2005, Lee, Pohlman et al. 2010). Additional details for each of these tests follow.

- **Inhibitory Control**

Stop Signal Test (SST). This task measures how long it takes for an individual to cancel an initiated motor response. On each of 256 trials a stimulus appears, and subjects must press a corresponding key as quickly as possible. Subjects are, however, also instructed to try to stop themselves from completing a response if they hear a “stop-signal” tone (25% of trials)

MATRICES Continuous Performance Test (MATRICS CPT-II). We will employ the Identical Pairs version CPT which is part of the MATRICS assessment battery (MATRICS, 2006). This is a computerized test of sustained attention and response inhibition which was developed at UCLA and has indices of response inhibition (commission errors), vigilance (omissions), and reaction time. The MATRICS CPT-II will be administered at baseline, week 4 and termination.

Connors' Continuous Performance Test (Connors' CPT-II). The Connors' CPT-II is a reliable and valid computer administered test of sustained attention that takes approximately 15 minutes to administer. The Connors' CPT-II will be administered at weeks 2, 6 and 10.

- **Risk Taking/Decision Making**

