APPENDIX II: Assessment Schedule for Ibudilast Phase 2 Trial

STUDY ASSESSMENT TABLE FOR IBUDILAST PHASE II TRIAL

Measures	Baseline	Medication Phase			Follow-Up
		Weekly Wks 1-12	Specific time	Monthly Wk 4, 8, 12	
	0.6 visits				Weekly Wk 13, 14, 15, 16
Clinical measures					
Medical history	X				
Physical	X				wk 13
EKG	X		wks 3, 8		wk 13
Labs	X		wks 3, 8		wk 13
HCV serology	X				wk 13
HIV test	X				wk 13
if HIV+, CD4/viral load	X				wks 13, 16
DNA/SNP sample	X				
Inf/NT markers (serum and plasma)	X		wks 3, 8		wk 13
Pregnancy test	X			X	
Adverse events	X	X			X
Urine drug screen	e	e			X
Vital signs	e	e			X
Progress note	e	e			X
Urinary cotinine	X	X			X
Concomitant medications	X	X			
Pill count		X			wk 13
HIV medication adherence	X			X	wk 16
Medication compliance (urine) via UV fluorimetry	e	e			wk 13
Stored urine aliquot	X	e			
Medication compliance (serum)			wk 3		
Behavioral assessments					
ASI	X				
BIS-11	X				
PSS-14	X				
ELSQ			wk 3		
PLC-C			wk 3		
SCID	X				
WURS	X				
HRBS	X			X	wk 16
BSI	X			X	wk 16
MA Craving VAS	X	X			X
C-SSRS	X	X			X
HAMD	X	X			X
TLFB	X (0.1, 0.4)	X			X
Medical Management Counseling	X	X			
Cognitive functioning measures After July 2016, only MOCA is still being administered					
WTAR	X				
WRAT4	X				
MOCA	X (0.1)		wk 4		wk 13
BVMT-R	X		wk 4		wk 13
HVLT-R	X		wk 4		wk 13
CPT-II (MATRICS version)	X		wk 4		wk 13
CPT-II (Connors' version)			wks 2, 6, 10		
TMT	X		wk 4		wk 13
SST (comp)	X		wk 4		wk 13
DDT (comp)	X		wk 4		wk 13
Iowa Gambling Task	X		wk 4		wk 13
Symbol Coding (WAIS-IV)	X		wk 4		wk 13
Symbol Search (WAIS-IV)	X		wk 4		wk 13
Letter Number Sequencing (WAIS-IV)	X		wk 4		wk 13
N-Back Task	X		wk 4		wk 13
DKEFS Color Word Interference	X		wk 4		wk 13
Pursuit Rotor Task	X		wk 4		wk 13

e: every visit.

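### The exploratory GEE of weekly cognitive change names one test that is not scheduled and one that is not scheduled weekly, so it cannot be run as written

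*Combined protocol and SAP*

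**What the plan says.** The combined protocol and SAP describes the serial cognitive tests in three ways.

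- **Data Analysis, Exploratory analyses.** "GEE models will be used to compare change in the brief serial weekly cognitive assessments (Balloon Analog Reaction Time task and Stop Signal test". The comparison is IBUD versus placebo during treatment.
- **Neuropsychological Assessment.** Beyond the pre/post battery, "brief serial assessments will be administered during the medication treatment period (weeks 1-12) to examine potential changes in both top-down (Iowa Gambling Task". The second serial test named there is Stop Signal. The Balloon Analog task is not named and no frequency is given. The same paragraph adds the Connors' CPT at weeks 2, 6 and 10.
- **Assessment of Neurocognitive Endophenotypes and Appendix II.** The repeat list reads "During weeks 4 and 13, participants will repeat the following tasks: Montreal Cognitive Assessment; MATRICS CPT-II; HVLIT-R; BVMT-R; SST; TMT; DDT", and it goes on to end with the Iowa Gambling Task. The Appendix II row for Stop Signal is "SST (comp) X wk 4 wk 13", with no mark in the weekly column. For the Connors' version, "The Connors' CPT-II will be administered at weeks 2, 6 and 10", and its baseline cell is empty.

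Two other analysis statements bear on the point. The exploratory section plans baseline-to-post-treatment change by arm, with effect sizes, for the neuropsychological battery. The opening of Data Analysis gives a general strategy of bivariate tests between arms on all outcome variables.

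**The concern.** A GEE for weekly change needs repeated on-treatment values of the tests it names. Here one named test has no place in the schedule and the other has a single scheduled value within the treatment weeks. The test that does form a series during medication is left out of the sentence that specifies the model.

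The stake is analyst discretion. If the sentence cannot be followed, the test, score, visits and model will be chosen later, possibly with results in view. The protocol says these exploratory probes may support any observed effect on methamphetamine use and inform the design of phase III, so the choice should be written down.

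**Working it through.** No alpha, power or sample-size figure is involved. The check compares the analysis text with the test descriptions, the repeat list, the reimbursement list and Appendix II, and counts scheduled administrations.

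**Step 1: what the analysis requires.** Weekly testing over weeks 1-12 means 12 on-treatment values per participant per test.

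**Step 2: what is scheduled** (repeat list, test descriptions and Appendix II).

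| Test | Baseline | Within weeks 1-12 | Week 13 | Count against 12 |
|---|---|---|---|---|
| Balloon Analog | not listed | none | not listed | 0 |
| Stop Signal | yes | week 4 | yes | 1 |
| Iowa Gambling | yes | week 4 | yes | 1 |
| Connors' CPT-II | no | weeks 2, 6, 10 | no | 3 |
| MATRICS CPT-II | yes | week 4 | yes | 1 |

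The Neuropsychological Assessment section places week 13 immediately after study medication stops, so week 4 is the only on-drug value for Stop Signal and Iowa Gambling. The remaining repeated tests in Appendix II also have week 4 as their only visit during medication. The Connors' CPT-II is therefore the only cognitive test scheduled more than once in that period.

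**Step 3: could a paid task be missing from the lists?** The reimbursement items reproduce the stated totals.

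- Without cognitive testing: 80 + 25 + 60 + 200 + 100 + 30 + 15 = 510 dollars.
- Adding the Connors' CPT (15) and the battery (40): 510 + 15 + 40 = 565 dollars.
- Adding Iowa Gambling (30): 565 + 30 = 595 dollars.

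All three agree with Table 4, so no paid Balloon Analog session is missing. This does not exclude unpaid serial Stop Signal testing, because Stop Signal has no payment line of its own.

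**Step 4: which analyses can reach each test?**

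- Balloon Analog: none, as no data are scheduled.
- Stop Signal and Iowa Gambling: the battery change analysis, since both are scheduled at baseline and week 13.
- Connors' CPT-II: the GEE sentence omits it, and baseline-to-post-treatment change cannot be computed because it has neither a baseline nor a week 13 administration. Only the general bivariate strategy could cover it, and that names no score, visit or repeated-measures model.

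**Step 5: size of the affected data.** Battery collection ended after 85 of 140 randomizations, and only the MoCA continued. The Connors' series holds at most 85 x 3 = 255 values before attrition.

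**The case against.** The strongest reply is that little depends on this sentence. It sits among analyses the protocol calls exploratory and not powered, and none of Aims 1-4 concerns serial cognition. The neurocognitive part of Aim 3 uses change from baseline to the end of medication and does not need the GEE. All of this stands and limits the weight of the point.

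A reader might infer that the plan cannot compare arms on inhibitory control or decision making at all. The document does not support that. Stop Signal and Iowa Gambling are collected three times, and their baseline-to-post-treatment change by arm falls under the battery analysis. A GEE on three Stop Signal occasions is also feasible; it would not be weekly.

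A reader might also infer that the Connors' series has no between-arm analysis, or that its missing baseline makes it unusable. The general bivariate strategy could cover it, and the GEE sentence speaks of change during treatment without requiring change from baseline. Randomization allows a comparison of levels, or of trend over weeks 2 to 10, without a baseline.

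Finally, Appendix II need not be right. The Neuropsychological Assessment section describes Stop Signal as a serial test in addition to the pre/post battery. That agrees in part with the GEE sentence and conflicts with the repeat list and Appendix II. The document does not show which reflects conduct, so the request must be to reconcile them.

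None of this rescues the sentence as written. The Balloon Analog task is still unscheduled, and weekly Stop Signal testing appears in neither the repeat list nor Appendix II.

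**Conclusion.** The point holds as a mis-specified exploratory analysis. The weekly GEE cannot be run as written: 0 of 12 implied on-treatment values are scheduled for the Balloon Analog task and 1 of 12 for Stop Signal. The one series that is scheduled, the Connors' CPT-II with 3 values, has no specific analysis. What is lost is a prespecified on-treatment trajectory in at most 85 participants. The primary outcome, retention, the HIV aims and the battery change analysis are unaffected.

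The conclusion assumes that the repeat list and Appendix II, which agree with each other on Stop Signal and Iowa Gambling, describe what was done. If serial Stop Signal data were collected as the Neuropsychological Assessment section suggests, a GEE on that test could be kept at the visits actually held. The Balloon Analog task would still need to be removed, and the Connors' series would still need a stated analysis.

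**What to change.** 1. Reconcile Neuropsychological Assessment, the repeat list, Exploratory analyses and Appendix II on which serial tests were given and at which visits. Keep or drop the description of Stop Signal as serial or weekly according to what was done.
2. Remove the Balloon Analog task from the GEE sentence.
3. Specify a GEE or mixed model with arm, week and arm-by-week terms for the Connors' CPT-II at weeks 2, 6 and 10, naming the score, and compare levels and trend between arms. The baseline MATRICS CPT-II may be added as a precision covariate. This is optional: it is a different version of the test, and the document gives no correlation between the two.
4. Analyse Stop Signal and Iowa Gambling at their scheduled visits (weeks 4 and 13 in Appendix II), each adjusted for its own baseline.
5. Label all of this exploratory and state the denominator as at most 85 participants before attrition.

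The cost is protocol and SAP wording. No visit or test is added, and the data come from participants already scheduled for cognitive testing. The change should be dated and made before treatment codes are opened for these outcomes.
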